20.3. Listing Mock-Ups51

1. GLOSSARY OF ABBREVIATIONS

Abbreviation	Description
ACT	Assessment of Current Therapy
AE	Adverse event
ALT	Alanine transferase
AP	Alkaline phosphatase
AST	Aspartate aminotransferase
ATC	Anatomical Therapeutic Chemical
BP	Blood Pressure
BUN	Blood Urea Nitrogen
C	Celsius
cm	Centimeter
CPK	Creatinine phosphokinase
CTM	Clinical trial material
CRF	Case report form
DBP	Diastolic Blood Pressure
ECG	Electrocardiogram
GCP	Good Clinical Practice
GGT	Gamma-glutamyltransferase
HDL	High-density lipoprotein
HR	Heart rate
ICF	Informed consent form
ICH	International Conference on Harmonisation
INR	International Normalized Ratio
Kg	Kilogram
LDH	Lactate dehydrogenase

Abbreviation	Description
LDL	Low-density lipoprotein
M207	Intracutaneous Microneedle System (M207)
MBS	Most Bothersome Symptom
Mg	Milligrams
mITT	Modified Intent-to-Treat
mL	Milliliter
NSAID	Nonsteroidal anti-inflammatory drug
PCP	Phencyclidine
PE	Physical examination
PT	Preferred Term or Prothrombin
RR	Respiratory Rate
SAE	Serious Adverse Event
SAP	Statistical Analysis Plan
SBP	Systolic Blood Pressure
SD	Standard deviation
SGPT	Serum glutamic pyruvic transaminase
SGOT	Serum glutamic oxaloacetic transaminase
SNRI	Serotonin-norepinephrine reuptake inhibitors
SOC	System Organ Class
SSRI	Selective serotonin reuptake inhibitors
TEAE	Treatment-emergent adverse event
TLFs	Tables, Listings, and Figures
WOCBP	Women of child-bearing potential

2. PURPOSE

The purpose of this statistical analysis plan (SAP) is to ensure that the data listings, summary tables and figures which will be produced, and the statistical methodologies that will be used, are complete and appropriate to allow valid conclusions regarding the study objectives.

2.1. RESPONSIBILITIES

Syneos Health will perform the statistical analyses and are responsible for the production and quality control of all tables, figures and listings (TLFs).

2.2. TIMINGS OF ANALYSES

The final analysis will be conducted by Syneos Health after all subjects complete the final study visit or terminate early from the study, and the database has been locked.

3. STUDY OBJECTIVES

3.1. PRIMARY OBJECTIVE

To assess the long-term safety of 3.8 mg (administered as two 1.9 mg patches) of M207 for the acute treatment of migraine.

3.2. SECONDARY OBJECTIVES

To assess the efficacy of 3.8 mg (administered as two 1.9 mg patches) of M207 for the acute treatment of migraine.

3.3. BRIEF DESCRIPTION

This is an open-label, twelve-month safety study. There is a screening period followed by a run-in period (14 to 21 days) to determine eligibility for treatment with study medication based on daily eDiary data collection. Qualified subjects will receive study medication on Day 1 for up to twelve months for the treatment of migraine headaches. Migraines will be treated with a single dose, consisting of two patches, but subjects can treat multiple migraine attacks throughout the 12 months. Using the eDiary to confirm they are experiencing a qualified migraine, subjects will self-administer the patches and continue to respond to questions in the eDiary for 48 hours post treatment administration.

3.4. SUBJECT SELECTION

Approximately 400 subjects will be screened to ensure that at least 300 subjects enter the run-in period and that at least 250 subjects are enrolled into the treatment phase. Fifty subjects must complete the entire one-year treatment period and 150 subjects must complete a minimum of six months of treatment.

3.4.1. Inclusion Criteria

The inclusion criteria are detailed in Sections 3.2.2 of protocol amendment 2.0

3.4.2. Exclusion Criteria

The exclusion criteria are detailed in Sections 3.2.3 of protocol amendment 2.0

3.5. DETERMINATION OF SAMPLE SIZE

The sample size chosen for this study was selected without statistical considerations. It has been determined adequate to meet the study objectives.

3.6. TREATMENT ASSIGNMENT & BLINDING

This study is an open label study. There is no blinding of treatment assignment in this study.

3.7. ADMINISTRATION OF STUDY MEDICATION

All subjects in the study will receive open label M207, 3.8 mg to administer as two 1.9 mg patches to treat each qualified migraine during the study.

There are two types of M207 kits for each subject, starter kits and refill kits, clearly labeled and visually distinguishable. Each M207 Clinical trial material (CTM) kit includes either 4 (starter kit) or 8 (refill kit) individual foil pouches or cups. Each pouch or cup contains one patch. The starter kit dispensed on day 1 contains the applicator. Refill kits will be dispensed as needed throughout the study. A replacement applicator will be issued at approximately six months, and or/as needed if a previously dispensed applicator is defective or lost.

At each medication dispensation visit, after it has been established that a subject continues to qualify for the study, study staff will document the total number of patches dispensed to each subject and unopened (unused) patches returned at each visit in the electronic case report form (eCRF) and drug accountability records.

3.8. STUDY PROCEDURES AND FLOWCHART

All study visits and procedures will be performed according to the Schedule of Study Procedures as listed in Table 1. Subject visits should be scheduled as soon as possible within the specified windows.

A screening visit 1 will be conducted up to one week prior to start of the run-in-period.

The following assessments will be performed at screening to determine subject's eligibility. Demographic data (including name, sex, age, race, ethnicity, height, and weight), Fitzpatrick Skin Scale Questionnaire, Medical history, Migraine History, Prior and concomitant medications, Physical Examination (PE) including body weight (kg), height (cm) and BMI (kg/m^2) will be reported. Each subject will have vital sign measurements; heart rate (HR), blood pressure (BP), temperature (TEMP), and respiratory rate (RR), 12-lead Electrocardiogram (ECG), laboratory tests for hematological, chemistry, and additional laboratory tests.

A screening visit 2 (start of run-in-period) will be conducted within two to three weeks prior to dispensation of study medication.

The following assessments and activities will be performed during visit 2. Vital sign measurements (HR, BP, TEMP, and RR), Concomitant medications, training of eDiary, and dispense of eDiary.

Table 1: Schedule of Study Procedures

	VISIT 1 ¹ Screening	VISIT 2 ¹ Start of Run- In	VISIT 3	VISIT 4, 5, 6	VISIT 7	VISIT 8	VISIT 9 Final visit or ET	VISIT 10 Two Week Post Study Visit
Procedure	Up to 1 week prior to Run-in	Week -2 (up to -3)	Day 1 (dispense patches)	Month 1, 2, 3	Month 6	Month 9	Month 12	Two Week Safety visit
Day/Visit Windows				Day 28, 56, 84 ± 7 days	Day 168 ± 7 days	Day 252 ± 7 days	Day 336 ± 7 days	14 (+ up to 14) days following final visit or ET
Week				Week 4, 8, 12	Week 24	Week 36	Week 48	Week 50 - 52
Informed Consent	X							
Inclusion/Exclusion/ Eligibility Criteria	X	X	X					
Med History/ Migraine History	X							
Fitzpatrick Skin Scale (subject completed)	X							
Demographics	X							
Physical Exam ³	X		X		X		X	
Weight/Height (Height only at screen and final visit or ET) ⁴	X		X	X		X	X	
Vital Signs ⁵	X	X	X	X	X	X	X	X
Lab Chem/Hematology (fasting)	X ⁶						X	
Serum or Urine Pregnancy (only for WOCBP)	X - Serum		X - Urine	X - Urine	X - Urine	X - Urine	X - Urine	
Drug Abuse Testing	X				X		X	
12-lead ECG	X				X		X	
Train Subject on How to Apply Patches (using demo patches)		X	X					
Train/dispense eDiary		X	X					
Dispense Study Medication			X	X	X	X		
Study Drug Self-							→	

	VISIT 1 ¹ Screening	VISIT 2 ¹ Start of Run- In	VISIT 3	VISIT 4, 5, 6	VISIT 7	VISIT 8	VISIT 9 Final visit or ET	VISIT 10 Two Week Post Study Visit
Procedure	Up to 1 week prior to Run-in	Week -2 (up to -3)	Day 1 (dispense patches)	Month 1, 2, 3	Month 6	Month 9	Month 12	Two Week Safety visit
Administration								
Subject eDiary Reported Skin Assessments							→	
Migraine-ACT (subject completed)				X	X	X	X	
Investigator Skin Assessments				X	X	X	X	X
Monthly phone contacts to subject ⁷							→	
Collect Unused Patch(es)/Perform Drug Accountability ⁸				X	X	X	X	
Collect and Review eDiary data			X	X	X	X	X	
Record Adverse Events	X	X	X	X	X	X	X	X
Record Concomitant Medications	X	X	X	X	X	X	X	X

¹ Visit 1 and Visit 2 may be combined into one visit. On the day of screening procedures, if preliminary entry criteria indicate that the subject is probably eligible, the eDiary can be issued and the subject may begin the run-in period. If during the run-in period, additional information becomes available to exclude the subject (e.g., return of 12-lead ECG or lab results), the subject should be notified of screen failure and instructed to return any provisional eDiary device (if applicable) to the center.

³ Physical exam to include (but not limited to) HEENT, Dermatologic, Neurological, General Appearance, Lymph Nodes, Cardiovascular, Respiratory, Gastrointestinal, and Musculoskeletal

⁴ Weight at each visit; both height and weight to be collected at screening and final visit only (or early termination visit)

⁵ Vital signs include temperature, respiratory rate (RR), blood pressure (BP), and heart rate (HR)

⁶ Clinically significant abnormal values may be repeated to confirm eligibility

⁷ Phone contacts monthly at months 4, 5, 7, 8, 10, and 11 to remind subjects to treat at least two migraine attacks per month and to assess for adverse events and concomitant medication use

⁸ Subjects may return for an unscheduled visit to pick up additional study medication as needed.

4. ENDPOINTS

4.1. EFFICACY ENDPOINTS

- Proportion of Migraines that are pain free at 30 minutes, 2 hours, 12 hours, 24 hours, and 48 hours post-dose
- Proportion of subjects with pain freedom at 30 minutes, 2 hours, 12 hours, 24 hours, and 48 hours post-dose for the 1st, 5th, 15th, and 25th migraine a subject experiences
- Proportion of migraines with most bothersome other symptom freedom at 30 minutes, 2 hours, 12 hours, 24 hours, and 48 hours post-dose
- Proportion of subjects with most bothersome other symptom freedom at 30 minutes, 2 hours, 12 hours, 24 hours, and 48 hours post-dose for the 1st, 5th, 15th, and 25th migraine a subject experiences
- Proportion of migraines with pain relief at 30 minutes, 2 hours, 12 hours, 24 hours and 48 hours post-dose
- Proportion of migraines with nausea freedom at 30 minutes, 2 hours, 12 hours, 24 hours and 48 hours post-dose
- Proportion of migraines with photophobia freedom at 30 minutes, 2 hours, 12 hours, 24 hours and 48 hours post-dose
- Proportion of migraines with phonophobia freedom at 30 minutes, 2 hours, 12 hours, 24 hours and 48 hours post-dose
- Proportions of migraines that require rescue medication within 2 hours post-dose
- Proportion of migraines that recurred within 24 and 48 hours post-dose
- Proportion of migraines with sustained pain freedom from 2 to 24 hours post-dose and from 2 to 48 hours post-dose
- Frequency of responses on the migraine assessment of current therapy (ACT)

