3.2 Selection of Study Population

3.2.1 Number of Subjects

Approximately 400 subjects will be screened to ensure that at least 300 subjects enter the run-in period and that at least 250 subjects are enrolled into the treatment phase. Fifty subjects must complete the entire one-year treatment period and 150 subjects must complete a minimum of six months of treatment.

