3.2.2 Inclusion Criteria

Subjects presenting with all of the following may be included in the study:

1. Able to provide written informed consent
2. Women or men 18 to 75 years of age
3. Greater than 1 year history of episodic, migraine (with or without aura) with onset prior to 50 years of age. Diagnosis must comply with International Headache Society (IHS ICHD-3beta) diagnostic criteria. Diagnostic criteria must include a history of at least five attacks not attributed to any other disorder that include all of the following criteria:
 - a) Headache attacks lasting 4-72 hours (untreated or unsuccessfully treated)
 - b) Headache has at least two of the following characteristics:
 - i. unilateral location
 - ii. pulsating quality

- iii. moderate or severe pain intensity
- iv. aggravation by or causing avoidance of routine physical activity (e.g., walking or climbing stairs)
- c) During headache at least one of the following:
 - i. nausea and/or vomiting
 - ii. both photophobia **and** phonophobia
- 4. Migraine history during the 6-month period prior to the screening period must include:
 - a) at least 2 migraines per month
 - b) no more than 8 migraines per month
 - c) no more than 15 headache days per month
- 5. Women of child-bearing potential must not be pregnant, must agree to avoid pregnancy during the trial, and must use an acceptable double-barrier method of birth control (examples of methods include partner using condom, female using IUD, hormonal or non-hormonal contraceptive, diaphragm with spermicide, or contraceptive sponge) for the duration of the trial.
- 6. No significant ECG findings, defined by:
 - a) ischemic changes defined as > 1 mm of down-sloping ST segment depression in at least two contiguous leads,
 - b) Q-waves present in at least two contiguous leads,
 - c) clinically significant intra-ventricular conduction abnormalities (left bundle branch block or Wolf-Parkinson-White syndrome), or
 - d) clinically significant arrhythmias (e.g., current atrial fibrillation)
- 7. Able to understand and operate the electronic diary
- 8. Able to apply the demo study drug patches
- 9. In the opinion of the investigator, subject is willing to treat a minimum of 2 migraines per month with use of study medication and is willing to consistently perform eDiary completion for up to 12 months.

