3.2.6.2 Replacement of Subjects

Subjects who discontinue after starting treatment but before six months will be replaced to ensure adequate enrollment, i.e., 150 subjects in the study who complete six months and 50 subjects who complete a year.

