8.1. EFFICACY ENDPOINTS AND ANALYSIS

The following efficacy endpoints will be summarized using descriptive statistics:

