8.1.1. The Proportion of Migraines and Subjects Experiencing Pain Freedom

The proportion of subjects who are pain-free without the use of rescue medication (i.e., a pain severity score of 0 and no rescue medication reported within the given timeframe) at 30 minutes, 2 hours, 12 hours, 24 hours, and 48 hours after dosing for the 1st, 5th, 15th, and 25th migraine a subject experiences will be summarized descriptively;

The proportion of migraines that are pain-free without the use of rescue medication (i.e., a pain severity score of 0 and no rescue medication reported within the given timeframe) at 30 minutes, 2 hours, 12 hours, 24 hours, and 48 hours after dosing will be summarized descriptively.

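### Response at the 1st, 5th, 15th and 25th migraine is computed in different, shrinking groups of subjects, so a flat or rising series does not show that the effect is maintained

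*SAP*

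**What the plan says.** SAP 4.1 lists pain freedom and MBS freedom as per-subject endpoints "for the 1st, 5th, 15th, and 25th migraine a subject experiences". SAP 8.1.1 states that the proportion of subjects who are pain-free without rescue medication, at five times after dosing, "for the 1st, 5th, 15th, and 25th migraine a subject experiences will be summarized descriptively". SAP 8.1.2 does the same for MBS freedom and restricts it to attacks where the symptom was present before dosing. SAP 13 records that both by-number endpoints were added to the protocol's set. SAP 8.1 sets the level of inference: "The following efficacy endpoints will be summarized using descriptive statistics".

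The denominator follows from general rules. SAP 15.2.5.2 bases percentages on subjects who have an observation, SAP 6.3 imputes nothing unless otherwise specified, and SAP 6.6 plans no subgroup analysis. The table index (SAP 17) lists by-number tables for pain freedom (14.2.1.1.2) and MBS (14.2.1.2.2). No title there describes the same subjects followed across the four migraine numbers.

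On numbers, SAP 3.4 requires that "at least 250 subjects are enrolled into the treatment phase", and Protocol 3.2.1 says "Fifty subjects must complete the entire one-year treatment period and 150 subjects must complete a minimum of six months of treatment". Protocol 3.2.6.2 adds: "Subjects who discontinue after starting treatment but before six months will be replaced to ensure adequate enrollment". SAP 3.5 gives no statistical basis for the size: "The sample size chosen for this study was selected without statistical considerations".

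**The concern.** A reader will naturally take four rates by migraine number as a statement about repeated use. A flat line suggests that the effect holds; a rising line suggests that it improves. But a subject appears at the 25th migraine only after having enough attacks and staying on treatment long enough, and neither need be independent of response.

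Several mechanisms decide who is left. Protocol 3.2.2 admits subjects with "at least 2 migraines per month" and at most 8, a fourfold range. Protocol 3.2.6.1 allows withdrawal for fewer than 6 qualifying migraines in 12 weeks, at the subject's request, for adverse events and for non-compliance. The treatment period itself is 6 to 12 months. If non-responders leave sooner, the later rates rise with nobody improving, and a modest loss of effect can be masked.

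There is also a wording gap. The index counts migraines experienced, but post-dose data exist only for treated ones. Under Protocol 6.1.4 an attack within 48 hours of a previous application cannot be treated, and one already medicated that day does not qualify. Two programmers could number the same subject differently.

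**Working it through.** The plan gives no sample-size calculation, effect size or dropout rate for this endpoint, so there is no stated figure to reproduce.

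**Step 1: who can reach the 25th migraine.** Inputs: 2 to 8 migraines per month (Protocol 3.2.2); 336 days to Month 12 and 168 to Month 6 (Protocol Table 10); 30-day months (SAP 11.1).
- At 2 per month, the expected count over 336 days is 2 × 336/30 = 22.4, or 24 if a month is 28 days. Both are below 25. The 15th takes 15/2 = 7.5 months.
- If counts are Poisson (an assumption), P(N ≥ 25) is 0.319 at mean 22.4. At 2 per month over 168 days the mean is 11.2 and the probability is below 0.001. At 4 per month over 168 days the mean is again 22.4, giving 0.319.
- A subject who stops at 6 months needs 25/6 = 4.2 attacks per month.

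The 25th-migraine group is therefore weighted towards frequent attackers and long stayers.

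**Step 2: group sizes.** Starting from 250, with retention set to the floors of 150 (60%) at 6 months and 50 (20%) at 12 months, and attack rates either uniform on 2–8 per month or skewed low with mean 3.5 (assumed), simulation gives about 250, 221–233, 163–191 and 104–146 subjects at the 1st, 5th, 15th and 25th.

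**Step 3: the series when no subject changes.** Assumptions not in the documents: attack rates uniform on 2–8 per month, between-subject correlation of response 0.3, mean response 42% (close to the 34/82 = 41.5% pain-free at 2 hours on 3.8 mg in Protocol Table 4), and monthly dropout that falls as a subject's own response probability rises.
- Dropout 18% falling to 2%: 42.1, 42.8, 45.8 and 48.3%, with n from about 249 to 134. False rise 48.3 − 42.1 = 6.2 points.
- Dropout 14% falling to 4%: false rise 3.8 to 3.9 points.
- A separate simulation with the same two gradients gave 5.7 and 3.5 points.
- With retention set to the floors and leaving unrelated to response: 41.9% to 42.0%, no bias.

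**Step 4: a waning effect.** Assume two classes of subject (80% and 14.3% responders), a hazard of leaving after a non-response ten times that after a response, and low attack rates. If the drug's excess over the 14.3% placebo rate (Protocol Table 4) shrinks by a quarter by the 25th migraine, the observed series is 41.1, 42.3, 42.2, 41.7%, while the full-cohort value falls from 41.6% to 34.8%. In the models run, a 50% loss shows as a fall to 28–31%, and a total loss as a fall to 13–14%.

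**Step 5: precision at the 25th.** The 95% half-width is 1.96 × √(0.415 × 0.585/n), which is 8.1 points at n = 143 and 9.3 at n = 108.

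**Step 6: does a fixed set remove the artefact?** With constant response within subject, uniform attack rates, correlation 0.3 and a threefold hazard of leaving after a non-response, subjects who reach the 25th give 44.8% at the 1st and 45.3% at the 25th, which is essentially flat. The changing groups give 41.3% to 45.3%.

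**The case against.** These are secondary, descriptive summaries in an open-label safety study. The SAP plans no test across migraine numbers and states no conclusion about durability. Counts at each point are already required (SAP 6.1 and 15.2.5.2), and disposition, reasons for leaving and subjects present at each visit are reported (SAP 7.1). The table shells are a separate document. All of this stands and limits the point to interpretation; but the reported n does not separate change within subjects from change in who is counted.

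Three stronger readings are tempting and are not supported.
- A reader might infer that the series could look flat with the effect gone. In the models run, losses of half or more still show as a clear fall. Masking appeared only for a one-quarter loss under strong assumptions.
- A reader might infer that this is the only planned look at effect over time. It is not: Migraine-ACT responses are tabulated by visit (SAP 8.1.8), although attrition affects them too and they are not attack-level outcomes.
- A reader might infer that the bias must be upward because responders stay. The documents give no dropout rate and no link between response and leaving. If frequent attackers respond worse, the bias runs downward.

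The numbering point is minor. The endpoint is defined after dosing, and the exposure tables already count treated qualifying migraines, so the intent can be guessed. One sentence would settle it.

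**Conclusion.** The point holds as one of interpretation. That each rate describes a different group follows from the SAP's own denominator and missing-data rules and needs no assumption. The size does: about 3.5 to 6 points of false rise under the two assumed dropout gradients, none if leaving is unrelated to response, and possibly the opposite sign. An artefact of that size is below the 8-to-9-point half-width at the 25th migraine, so it would not stand out from noise, but neither could a flat or rising series be read as evidence of maintained effect. The change is worth making before database lock because it is cheap and uses data already collected.

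**What to change.** - State in SAP 4.1, 8.1.1 and 8.1.2 that the index counts treated qualifying migraines.
- Keep the planned tables. Add one block to Tables 14.2.1.1.2 and 14.2.1.2.2: the four rates in the fixed set of subjects who treated at least 25 migraines, and the 1st, 5th and 15th rates in the fixed set who treated at least 15.
- Base any statement on persistence on these fixed sets, worded as persistence among continued users and not among all who started.
- Footnote the MBS table to say that denominators still vary within a fixed set, because the symptom must be present before dosing.

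The cost is one extra block in two existing tables, with no new data. The downside is that the fixed sets say nothing about subjects who left, and their level can sit above that of the starting cohort (about 45% against 41% in Step 6).

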4.2. SAFETY ENDPOINTS

- Changes from baseline in physical examination findings at Months 6 and 12
- Changes from baseline in vital signs at Months 1, 2, 3, 6, 9, 12, and at the 2-week post-study visit
- Changes from baseline in clinical laboratory parameters at Month 12
- Changes from baseline and/or shifts in 12-lead ECG parameters at Months 6 and 12
- Frequency of concomitant medications

- Incidence of treatment-emergent systemic and skin AEs (TEAEs)
- Frequencies of type of redness, severity of swelling, amount of bruising, and amount of bleeding (30 minutes only) at the application site as reported by the subject at 30 minutes, 2 hour, 12 hour, 24 hour, and 48 hours post-dose
- Frequencies of amount of skin itching and severity of pain at the application site as reported by the subject at 48 hours post-dose
- Frequencies of amount of bruising, erythema, and edema at the application site as assessed by the Investigator at Months 1, 2, 3, 6, 9, 12, and at the 2-week post-study visit
- Proportion of subjects with presence of skin signs and symptoms as assessed by the Investigator at Months 1, 2, 3, 6, 9, 12, and at the 2-week post-study visit

